#### Dates of findings (Physical exams, ECG, LAB, Vital Signs and Questionnaires)

- If the assessment date (--DTC) is partial
  - If only the day is missing, it will be imputed to the 15th of the month unless month and year are the same as month and year of the visit date then impute visit date
  - If day and month are missing, it will be imputed to the 15th of June unless year is the same as year of the visit date then impute visit date
- If the assessment date (--DTC) is missing, it will be imputed with the visit date.

#### Diary Data

Two methods will be applied:

- 0-imputation: Patches without assessable duration are imputed as 0 hours.
- No imputation will be performed on time of application/removal unless explicitly described for specific analyses.

#### 5.2.5 Subgroup Efficacy Analysis/es

Analyses of continuous variables will in general include the baseline value as a covariate and treatment group as a factor. The randomization was stratified by center for logistic reasons only. Hence, center will in general not be considered as a factor in the statistical analysis models.

CONFIDENTIEL / Ne pas diffuser sans autorisation de DBV

CONFIDENTIAL / Do not distribute without DBV authorization

	Statistical Analysis Plan	
	EPITOPE (V712-304) – Statistical Analysis Plan	
	Référence du Document /Document Reference : CCI	Page : 23 / 74

CCI

The following subgroups will be defined:

- Screening ED group (ED  $\leq$ 10 mg, ED >10 mg)
- Age group (1-year, 2-years, 3-years)
- IgE levels at screening
  - <17.5 kU/L, 17.5 to 50 kU/L, 50 to 100 kU/L, >100 kU/L
  - <17.5 kU/L,  $\geq$  17.5 kU/L
  - <100 kU/L,  $\geq$  100 kU/L
- Region (Australia, Europe, North America)
- Gender (Male, Female)
- Race (White, Black or African American, Asian, Other [incl. American Indian or Alaska Native, and Native Hawaiian or Other Pacific Islander], not collected)
- Ongoing Medical history of asthma at baseline (Yes / No)
- Ongoing Medical history of allergy other than peanut at baseline (Yes/No) (see section 5.3.4)
- Ongoing Medical history of food allergy other than peanut at baseline (Yes / No) (see section 5.3.4)
- Ongoing Medical history of eczema/atopic dermatitis at baseline (Yes / No) (see section 5.3.4)
- Ongoing Medical history of rhinitis allergic at baseline (Yes / No) (see section 5.3.4)

Subgroup analyses of the primary and secondary efficacy endpoints will be performed as specified in the respective sections below. Analyses with subgroups containing less than 15 subjects should be interpreted with caution.

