#### 4.1 Inclusion Criteria

Subjects will be enrolled only if they meet all of the following criteria:

1. Male or female from 1-3 years of age at Visit 1.
2. Physician-diagnosed peanut allergy or high suspicion of peanut allergy as assessed by the physician: child presenting signs, symptoms and a medical and/or a family history putting him/her at high risk of having a peanut allergy and/or history of presence of peanut-specific IgE and/or positive SPT.
3. Subject currently following a strict peanut-free diet.
4. Signed informed consent of parent(s)/guardian(s) of the children aged 1-3 years.
5. Peanut-specific IgE level (ImmunoCAP system) > 0.7 kU/L.
6. Positive peanut SPT with a largest wheal diameter  $\geq 6$  mm.
7. Positive DBPCFC to peanut, with symptoms meeting the challenge stopping criteria at an ED  $\leq 300$  mg peanut protein.
8. Parents/guardians and subjects willing to comply with all study requirements during their participation in the study.

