## 5 STATISTICAL METHODOLOGY

### 5.1 General considerations

The following conventions will be used when presenting summary statistics and analyzing continuous study data:

- Continuous data will be summarized in terms of number of subjects or observations with non-missing data (n), mean, standard deviation (SD), first quartile (Q1), median, third quartile (Q3), minimum (min) and maximum (max), unless otherwise stated.
- For data not normally distributed, a log transformation will be implemented before analysis.
- Compared to the number of decimals recorded for the raw data in the database, the statistics will be reported with the following number of decimals, unless otherwise specified:
  - Minimum and maximum: same number
  - Mean, median, Q1, Q3: one extra decimal
  - Standard deviation: two extra decimals.
- For any parameter at a specific visit or timepoint:
  - Change from Baseline will be calculated as the value of that parameter at that visit minus the Baseline value of that parameter

CONFIDENTIEL / Ne pas diffuser sans autorisation de DBV

CONFIDENTIAL / Do not distribute without DBV authorization

	Statistical Analysis Plan	
	EPITOPÉ (V712-304) – Statistical Analysis Plan	
	Référence du Document /Document Reference : CCI	Page : 18 / 74

CCI

- Relative change from Baseline will be calculated as the value of that parameter at that visit minus the Baseline value of that parameter divided by the Baseline value of that parameter multiplied by 100.
- For laboratory parameters, values below a detection limit or above a specific value (e.g. <0.35 kU/L or >100 kU/L) will be considered as equal to that limit/value (e.g. =0.35 or 100) in the statistical analyses (except in listing where the reported value will be presented).

In case of change of detection limit during the course of the study (e.g. from <0.35 kU/L to <0.1 kU/L), all values lower than the highest limit value will be imputed to this threshold (e.g. all values lower than 0.35 kU/L will be considered as equal to 0.35 kU/L). This conservative approach will ensure that changes from Baseline are consistent.

The following conventions will be used when presenting summary statistics for categorical study data:

- Categorical data will be summarized in terms of the number of subjects or observations providing non-missing data at the relevant time point (n), frequency counts and percentages. Any planned collapsing of categories will be detailed in the SAP text and the data displays.

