No imputation will be performed for other efficacy, safety and exploratory parameters. In those instances, observed data will be used, excepted for laboratory results reported as below the lower detection limit (or reported above a specific value) which will be imputed as described in Section 5.1 and safety data where partial or missing data will be imputed according to the most conservative approach. (See section 5.5.1.2).

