#### 5.3.3.2 Baseline Characteristics

Descriptive statistics will be produced for baseline characteristics by treatment group and overall. Baseline characteristics data include:

- Height (cm), Weight (kg)
- Peanut-specific IgE (kU/L)
- Peanut-specific IgG4 (mg/L)
- Skin Prick Test (SPT): Mean and longest wheal diameter for undiluted peanut extract (mm)
- ED in continuous
- ED in categories:
  - 1, 3, 10, 30, 100, 300 mg;
  - < 10mg, ≥ 10mg
- CRD in continuous

Summaries will be provided for the FAS. The full baseline characteristics data will be presented in a listing.

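### If 100 kU/L is the IgE reporting limit, the SAP's capping rule empties the >100 kU/L subgroup into the 50 to 100 class; a value of exactly 50 falls in two classes either way

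*SAP*

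**What the plan says.** SAP 5.2.5 lists "IgE levels at screening" among the subgroup factors and groups it in three ways. The first has four classes: "<17.5 kU/L, 17.5 to 50 kU/L, 50 to 100 kU/L, >100 kU/L". The second splits at 17.5 kU/L and the third at 100 kU/L; in both, the cut-point itself goes to the upper group.

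SAP 5.1 has a general rule for laboratory results outside the reportable range: "values below a detection limit or above a specific value (e.g. <0.35 kU/L or >100 kU/L) will be considered as equal to that limit/value". Its scope is wide. It applies "in the statistical analyses (except in listing where the reported value will be presented", so listings are the only exception. The last paragraph of SAP 5.2.4 points back to this rule for results below detection, "or reported above a specific value) which will be imputed as described in Section 5.1", and SAP 5.4.3 does the same. SAP 5.2.5 does not say that subgroup membership is decided on the reported result instead of the analysed one.

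The subgroups are used in two places. The subgroup part of the primary analysis table in SAP 5.4.1 plans response rates, differences with 95% confidence intervals and a forest plot for them. SAP 5.5.1.3 repeats the overview of treatment-emergent adverse events for them.

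**The concern.** The two rules do not fit together at the top of the scale. One replaces a result above the ceiling by the ceiling. The other reserves its highest class for values strictly above 100. If the ceiling is 100, no analysed value can enter that class. The children it was meant to describe move down one class, where they are mixed with children whose IgE was measured between 50 and 100.

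The third grouping in the same list places a value of 100 in its upper group, so the same child counts as high in one display and as 50 to 100 in another. Separately, the middle classes share the boundary of 50.

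What is at stake is the labelling and content of rows in the subgroup forest plot and the subgroup safety tables. If nothing is changed, a programmer will either follow the text and produce a misleading row, or depart from it without a documented rule.

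**Working it through.** The plan gives no figure to reproduce here. The check is to pass test values through the SAP 5.1 rule and then through the SAP 5.2.5 classes.

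**Inputs**
- Classes: from SAP 5.2.5, taking both ends of 17.5 to 50 and of 50 to 100 as included, since nothing says otherwise.
- Ceiling: 100 kU/L, the example in SAP 5.1. This is an assumption. Protocol 4.1 names the assay ("Peanut-specific IgE level (ImmunoCAP system) > 0.7 kU/L"), but the visible text gives no upper reporting limit and no dilution rule.
- Analyte: taken to be peanut-specific IgE, which SAP 5.3.3.2 lists as "Peanut-specific IgE (kU/L". The subgroup line does not say which IgE it means.

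**Two readings of the rule**
- Reading A: every value above 100 is set to 100, so analysed value = min(result, 100).
- Reading B: only a result reported as >x is set to x; a measured number is left as it is.

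| Result (kU/L) | Analysed, A | Four-class, A | Analysed, B | Four-class, B | Split at 100, A and B |
|---|---|---|---|---|---|
| 17.5 | 17.5 | 17.5 to 50 | 17.5 | 17.5 to 50 | <100 |
| 49.9 | 49.9 | 17.5 to 50 | 49.9 | 17.5 to 50 | <100 |
| 50 | 50 | 17.5 to 50 **and** 50 to 100 | 50 | 17.5 to 50 **and** 50 to 100 | <100 |
| 99.9 | 99.9 | 50 to 100 | 99.9 | 50 to 100 | <100 |
| 100 | 100 | 50 to 100 | 100 | 50 to 100 | ≥100 |
| reported as >100 | 100 | 50 to 100 | 100 | 50 to 100 | ≥100 |
| 150 | 100 | 50 to 100 | 150 | >100 | ≥100 |
| reported as >500 | 100 | 50 to 100 | 500 | >100 | ≥100 |

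**Results**
1. Under reading A the >100 class has no members, and every child above 100 is in the 50 to 100 class.
2. Under reading B the >100 class has members only if the laboratory reports results beyond 100. If 100 is the reporting limit, it does not, and the class is again empty.
3. Under both readings a result reported as >100, or equal to 100, is in the 50 to 100 class of the four-class split and in the upper group of the split at 100.
4. Under both readings a value of 50 is in two classes. A value of 17.5 is in only one, so that boundary is sound.

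With the classes written as <17.5, 17.5 to <50, 50 to <100 and ≥100, each value in the table falls in exactly one class under either reading, and the top class agrees with the split at 100.

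**The case against.** The strongest reply is that the 100 kU/L ceiling is only an illustration. SAP 5.1 introduces it as an example, next to a lower limit of 0.35 that the same section says could change during the study. Protocol 6.4.1 sends the samples to a central laboratory, and sample handling is left to a Laboratory Manual that is not in these documents. The wording in SAP 5.2.4 refers to results reported as above a value, which fits reading B better than a cap on every measurement. That the authors wrote a >100 class at all is also consistent with a laboratory that can report higher values, though it does not prove it. This stands: the empty row depends on an assumption. It does not remove the inconsistency for results reported as >100 or equal to 100.

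The second reply is that the effect is confined to subgroup displays. A reader might infer that the plan gives no estimate for the most sensitised children. The documents do not support that, because the split at 100 puts every capped result in its upper group, and that group gets its own response-rate difference, confidence interval and adverse-event overview. Nor is the primary result at risk. These subgroups are supportive, lie outside the testing hierarchy in SAP Table 1 and carry no success criterion.

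Third, the overlap at 50 touches only a child whose value is exactly 50, and nothing suggests there would be many. That is also fair; it is a wording slip, but it needs no assumption about the assay.

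Finally, if 100 is the ceiling, a corrected top class contains the same children as the existing ≥100 group. That duplication is harmless, and it is better than two rows for high IgE that disagree.

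**Conclusion.** The point holds as a conditional. If 100 kU/L is the upper reporting limit, or if every value above 100 is capped, all children in the intended >100 class are analysed in the 50 to 100 class and the top row is empty. If the laboratory reports numbers above 100 and these are left alone, the >100 class is populated, and the inconsistency shrinks to results reported as >100 or equal to 100. The double assignment of 50 holds regardless.

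The documents give no IgE distribution, so the number of children affected cannot be stated. The consequence is minor: one of three IgE groupings, in supportive efficacy displays and the adverse-event overview, with the primary analysis and its success criterion unaffected. It is still worth correcting, because the SAP text as it stands can put children in the wrong row.

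**What to change.** In SAP 5.2.5, define the four classes as <17.5, 17.5 to <50, 50 to <100 and ≥100 kU/L. This removes the overlap, keeps capped results in the top class, agrees with the existing split at 100, and works whether or not the laboratory reports values above 100.

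In SAP 5.1, state the assay's actual upper reporting limit for IgE, and say whether the cap applies only to results reported as >x or to every value above the limit.

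The cost is one line of class definitions and one clarifying sentence. No data collection, sample size or inferential procedure changes, and no planned analysis is lost.

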## 5.2.6 Key dates, Relative days

### 5.2.6.1 Key dates

- **The date of first patch application** of each subject will be taken from the first exposure date from eCRF.
  - If only the day is missing, it will be imputed using the day of the latest date between the randomization date and the first dispensation date.
  - If day and month are missing, they will be imputed using the day/month of the latest date between the randomization date and the first dispensation date.
  - If the date is missing, it will be taken from first dispensation date.
- **The date of last patch application** of each subject will be taken from the last exposure date from eCRF.
  - If only the day is missing, it will be imputed to the last day of the month unless month and year are the same as month and year of study end date then impute study end date

CONFIDENTIEL / Ne pas diffuser sans autorisation de DBV

CONFIDENTIAL / Do not distribute without DBV authorization

	Statistical Analysis Plan	
	EPITOPE (V712-304) – Statistical Analysis Plan	
	Référence du Document /Document Reference : CCI	Page : 24 / 74

CCI

- If day and month are missing, they will be imputed to the 31st of December unless year is the same as year of study end date then impute study end date.
- If the date is missing because the subject was lost to follow-up, it will be derived from the study end date.
- **The study end date** will be derived as the study completion date or study discontinuation date from the disposition domain.
- If the date is missing, it will be derived as the last date available from the visits, the examination, the assessments.

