#### ***4.3.4 Data Collection and Follow-up after Withdrawal***

If a subject is prematurely withdrawn from the IMP for any reason before completing all study visits, the Investigator must make every effort to perform the evaluations described for the Early Termination Visit (see Section 7.2.12). The Investigator must furthermore complete all appropriate subject diary and e-CRF pages, providing the date and explanation for the subject’s withdrawal/discontinuation. When indicated, the Investigator must

arrange for appropriate follow-up and/or alternative medical care of the discontinued subject.

If the subject fails to attend a scheduled End of Study Visit, there will be at least two documented attempts to contact the subject's parents/guardians via telephone and written communication. If no reply is received, the subject will be considered as lost to follow-up.

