### 5.3.8 Study duration, treatment exposure and compliance

The overall study duration for each subject will be approximately 62 weeks (6-week screening period, 52-week treatment period and 4-week follow-up period).

Study duration (days) will be calculated as:

- End of study date - Date of informed consent +1.

Due to the Covid-19 pandemic, some visits were postponed, and study duration can exceed 62 weeks (6-week screening period, 12-month treatment period and 4-week follow-up period) for the concerned subjects. Study duration will be summarized for the Safety set overall and by treatment group. The number (%) of subjects with a study duration exceeding 62 weeks will also be tabulated.

Treatment exposure will be based on:

CONFIDENTIEL / Ne pas diffuser sans autorisation de DBV

CONFIDENTIAL / Do not distribute without DBV authorization

	Statistical Analysis Plan	
	EPITOPE (V712-304) – Statistical Analysis Plan	
	Référence du Document /Document Reference : CCI	Page : 33 / 74

CCI

- The exposure duration (in days, regardless of treatment interruption), calculated over the whole study period as:
  - Date of last patch application – Date of first patch application) +1,
- The total dose of peanut protein (in mg) received via the patch during the study, calculated over the whole study period as:
  - Exposure duration (in days) \* Actual treatment dosage

Exposure duration and total peanut protein dose will be summarized for the Safety set overall and by treatment group (except total peanut protein dose that will only be described for the active arm).

Number and percentage of subjects per category of exposure duration (in days) will be presented using the following categories:

- 0 to 6 months (Day 1 to Day 180),
- 6 to 12 months (Day 181 to Day 365),
- 12 to 18 months (Day 366 to Day 545),
- > 18 months (> Day 546)

The compliance (%) determined over the whole study period as:

$$100 \times \left( \frac{\text{Number of patches dispensed} - \text{Number of patches returned}}{\text{Exposure duration in days}} \right)$$

Global compliance will be summarized for the Safety set overall and by treatment group.

Treatment compliance will be summarized using frequency tables (<80%, 80% to 100%, >100) and by means of descriptive statistics (n, mean, SD, median, Q1, minimum, Q3, and maximum) with compliance > 100% set to 100%.

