If a subject did not bring back unused patches, the amount of patches that have been applied cannot be accurately assessed. During the Data Review Meeting, before database lock, each subject having unreturned kit will be evaluated and a decision will be taken whether the subject compliance should be considered as missing.

The study medication must be applied on the skin for 24 hours every day ( $\pm 4$  hours), except during the initiation of treatment, where the duration of application of the study medication will be progressively increased as follows:

- During the first week (from Day 1 through Day 7), the patches will be applied for 2 hours ( $\pm 30$  minutes) every day;
- During the second week (from Day 8 through Day 14), the patches will be applied for 4 hours ( $\pm 30$  minutes) every day;
- During the third week (from Day 15 through Day 21), the patches will be applied for 8 hours ( $\pm 1$  hour) every day;
- During the fourth week (from Day 21 through Day 28), the patches will be applied for 12 hours ( $\pm 2$  hours) every day;

CONFIDENTIEL / Ne pas diffuser sans autorisation de DBV

CONFIDENTIAL / Do not distribute without DBV authorization

	Statistical Analysis Plan	
	EPITOPE (V712-304) – Statistical Analysis Plan	
	Référence du Document /Document Reference : CCI	Page : 34 / 74

CCI

- From the fifth week onwards (Day 29), the patches will be applied for the entire 24 hours ( $\pm 4$  hours) every day.

The time to first 24 hours ( $\pm 4$  hours) patch application will be summarized by means of descriptive statistics (n, mean, SD, median, Q1, minimum, Q3, and maximum) and described using a Kaplan Meier curve.

The daily application duration (in hours) will be summarized descriptively using the subject e-diary data for the following periods:

- Overall,
- D1 to D7,
- D8 to D14,
- D15 to D21,
- D22 to D28,
- D29 to D90,
- D91 to D185,
- D186 to D275,
- D276 to D365,
- > D365,
- D29 to D365,
- > D29

If more than one patch is applied the same day, the daily duration considered is the cumulative application duration of these patches (if the end date/time of first patch is not documented, the application date/time of the next patch will be used for imputation).

The percentage of days with no patch application, per subject e-diary reported data, will also be tabulated, overall and for each of the above periods.

A patch will be considered as “applied” if the date and time of application is documented in the e-diary.

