**Table 3 - Intercurrent Event Types**

Label	Intercurrent Event Type	Comment (for main estimand)
Intercurrent event 1 (Early treatment Discontinuation before 12 Months*)	Treatment exposure < M12 and missing peanut DBPCFC	Subjects will be included in the FAS. Subjects will be considered as a non-responder.
Intercurrent event 2 (subject/caregiver refusing the Month 12 peanut DBPCFC)	Treatment exposure $\geq$ M12, subject had not started the peanut DBPCFC and refusing to ingest the peanut formula	Subjects will be included in the FAS. An imputation will be used for missing data.
Intercurrent event 3 (peanut DBPCFC initiated but not finished)	Child starting the DBPCFC and stopped without symptoms leading to ending the peanut DBPCFC (stopping rules) (e.g. refusing to ingest the peanut formula left due to fear, aversion)	Subjects will be included in the FAS. An imputation will be used for missing data.
Intercurrent event 4 (peanut DBPCFC completed at Month 12* falls outside the recommended time-window)	Delayed peanut DBPCFC completed at Month 12 (e.g. due to temporarily closed centers or postponed visits (COVID-19))	Subjects will be included in the FAS. Actual values will be used regardless of whether an intercurrent event has occurred.
Intercurrent event 5 (discontinuation at or after Month 12 * with Month 12 peanut DBPCFC missing)	Treatment exposure $\geq$ M12 but missing peanut DBPCFC (e.g. due to temporarily closed centers or postponed visits (COVID-19))	Subjects will be included in the FAS. An imputation will be used for missing data.

\*Month 12 time windows are comprised between 358 – 407 days (section 5.2.7).

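### For a child lost to follow-up, the SAP's substitute last-patch date can turn a non-responder into an imputed response if the disposition date is the day loss was declared

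*SAP*

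**What the plan says.** SAP 5.2.6.1 starts from the eCRF: the last patch date "of each subject will be taken from the last exposure date from eCRF". For a child lost to follow-up with no such date, the rule is: "If the date is missing because the subject was lost to follow-up, it will be derived from the study end date". The study end date, in turn, "will be derived as the study completion date or study discontinuation date from the disposition domain". Only if that is absent too does the section turn to observed contact: "If the date is missing, it will be derived as the last date available from the visits, the examination, the assessments".

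SAP 5.3.8 computes exposure as last patch date minus first patch date plus 1, ignoring interruptions. SAP 5.3.1 splits discontinuations at 358 days, and the footnote to SAP Table 3 starts the Month 12 window at the same figure. Event 1 in Table 3 is "Treatment exposure < M12 and missing peanut DBPCFC"; event 5 is the same missing challenge with exposure of at least Month 12. Under SAP Table 4, event 1 counts as a non-response and event 5 is multiply imputed from placebo children.

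Protocol 4.3.1 describes loss to follow-up as missed scheduled visits with no answer to telephone or written contact. It sets no rule for dating the loss.

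**The concern.** The strategy in SAP Table 4 is that a child who stops treatment before Month 12 has failed. Whether a child with a missing challenge falls under that strategy depends on exposure. For a lost child without an eCRF date, exposure depends on an administrative date. Loss is recognised only after a visit is missed and contact fails, so a date of declaration falls later than the last patch by an unknown interval. The visit schedule makes that interval longest just before the endpoint.

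Table 3 illustrates event 5 with closed centres and postponed visits, that is, children who finished treatment but could not be challenged. A family that disappeared after Month 9 is a different case.

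The consequences reach beyond the primary responder rate. For the eliciting dose and cumulative reactive dose, event 1 uses the modified baseline-carried-forward rule and event 5 uses placebo-based imputation (SAP 5.2.4, Tables 5 and 6), so both hierarchical secondary endpoints are touched. Exposure duration and total peanut protein dose (SAP 5.3.8) are overstated, and the child is tabulated as discontinuing at or after Month 12 (SAP 5.3.1).

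**Working it through.** **The plan's own figures.** The protocol synopsis (Number of Subjects, Part B) assumes 40% versus 10% response, 233 and 117 children, a Newcombe 95% lower bound of at least 15%, and power of at least 90% at 350. Exact binomial enumeration gives 90.9%, so 350 reproduces. With the Farrington-Manning interval now in the SAP it is 91.5%. These rates and arm sizes are used below.

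**Step 1: timing.** Counting the first patch as Day 1, exposure equals the study day of the last patch.

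- Visit 9 is Month 9 ±7 days: Day 270 (263 to 277).
- The last scheduled phone contact is at Month 7.5, so nothing is scheduled between Visits 9 and 10.
- Visit 10 is Month 12 ±7 days; its earliest day is 365 − 7 = 358, which is the exposure cut-off.
- Extra days needed to reach the cut-off from Visit 9: 358 − 270 = 88 (358 − 277 = 81 to 358 − 263 = 95).

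**Step 2: what the disposition date does.** Take a child whose last patch and last contact were on Day 270, with no eCRF last-exposure date and no challenge.

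| Disposition date holds | Exposure | Event | Expected response |
|---|---|---|---|
| Last contact, Day 270 | 270 | 1 | 0 |
| Nothing, so last visit or assessment is used | 270 | 1 | 0 |
| Declaration, e.g. Day 365 | 365 | 5 | about 0.10 |
| Declaration, e.g. Day 400 | 400 | 5 | about 0.10 |

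In the last two rows exposure is overstated by 365 − 270 = 95 days (95/270 = 35%) and 400 − 270 = 130 days (130/270 = 48%).

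**Step 3: shift in the primary difference.** Let r be the placebo response rate, and fA and fP the proportions of each arm moved from event 1 to event 5. Both arms are imputed from placebo, so the shift is r × (fA − fP). The planned r is 0.10; Protocol Table 7 also considers 0.20 and 0.30. The documents give no late-loss rates, so fA and fP are assumptions.

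| fA versus fP | r = 0.10 | r = 0.20 | r = 0.30 |
|---|---|---|---|
| 5% v 2% | +0.3 | +0.6 | +0.9 |
| 5% v 0% | +0.5 | +1.0 | +1.5 |
| 5% v 5% | 0 | 0 | 0 |
| 2% v 5% | −0.3 | −0.6 | −0.9 |

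(Percentage points; first row, 0.10 × 0.03 = 0.003.) The planned 10% already counts up to 15% drop-out as failure, so the rate among challenged placebo children could be 0.10/0.85 = 0.118. At 5% versus 2% that gives 0.118 × 0.03, or about 0.35 points.

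On that 0.118 basis, and ignoring imputation variance, Farrington-Manning power moves from 91.5% to 90.9% with 5% moved in both arms, and to 93.3% with 5% moved in the active arm only.

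**Step 4: the own-arm sensitivity analysis.** One sensitivity analysis in SAP 5.4.1 imputes missing responses from the child's own arm. It refers to all missing data but names only events 2 and 5; I read it as those two. The shift is then fA × pA − fP × pP, where pA and pP are the arm response rates. With an equal 5% moved and the planned rates, 0.05 × (0.40 − 0.10) = 0.015, or +1.5 points. Balanced loss does not cancel there.

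**The case against.** The strongest objection is that the path needs two conditions the documents do not establish: the eCRF last-exposure date must be missing because of the loss, and the disposition date must be the declaration date. If it is the last contact, or is itself missing, the child stays in event 1. This stands, and the point is therefore conditional.

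A reader might infer that loss after Visit 9 cannot be noticed before Day 358. The documents do not support that: unscheduled visits are allowed for adverse events, resupply and adhesion problems, and diary data may show a gap. Only scheduled contact is absent. Nor does the protocol's passage on documented contact attempts ("If no reply is received, the subject will be considered as lost to follow-up") settle the date. It concerns a missed End of Study Visit, after the Month 12 challenge.

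A reader might also infer that the true last patch is usually known. SAP 5.3.8 does count a patch as applied "if the date and time of application is documented in the e-diary". But Protocol 6.2.5 has parents bring the diary to each visit, and the SAP does not say that e-diary entries are sent remotely, so a lost child's last entries may be unavailable. Protocol 5.3 dispenses enough patches to reach the next visit, so some lost children may really have been treated to about Month 12.

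Finally, three sensitivity analyses in SAP 5.4.1 treat events 1, 2 and 5 alike: all as failures, all imputed from placebo, or all excluded. Each removes the event 1/5 distinction and would expose a material effect. None carries the success criterion; the primary analysis does.

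**Conclusion.** The concern holds as a conditional defect in a stated derivation. SAP 5.2.6.1 can place an early dropout under event 5, contrary to the strategy in SAP Table 4, if the eCRF date is missing and the disposition date is the declaration date. Each moved child gains about the placebo response rate rather than a full response. The likely effect on the primary difference is under about one point, and it arises only if late loss differs between arms.

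A reader might infer that the rule favours the active arm. The documents give no reason to expect more late loss there; equal loss leaves the difference unchanged and slightly lowers power, and more loss on placebo works against the product. A scenario such as 15% late loss on active versus 5% on placebo would give 0.10 × 0.10 = 1.0 point, up to 0.30 × 0.10 = 3.0, but it uses the whole planned 15% maximum drop-out on this one route and is not a realistic guide. The exposure and disposition errors, and the own-arm sensitivity result, do not need unequal loss.

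**What to change.** Replace the sentence in SAP 5.2.6.1 with wording to this effect: *for a subject lost to follow-up with no eCRF last-exposure date, the last patch date is the last application recorded in the e-diary; if no diary data are available, it is the last visit or phone contact at which patch use was documented; the date on which loss was declared is not used.* Classify intercurrent events 1, 2 and 5 from that date, and state what the disposition date holds for lost children. Settle this before unblinding.

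The cost is one sentence and a derivation from data already collected. A few children may move from imputed response to non-responder. Where diary data are unavailable, exposure may be understated for a child who kept using dispensed patches; for that child's own outcome this is the conservative direction, since the child is counted as a non-responder.
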